7.4 Clinical outcomes and covariates

Table 3. Individual-level data derived from PWCF and sites

© 2018 Sheffield Teaching Hospitals NHS Foundation Trust. All rights reserved.

- + Pseudomonas (or other microorganism) status will be checked together with the monthly prescription* Only required where PWCF indicates they have received parenteral antibiotics

 ** EQ5D-5L collected at: the start and end of every exacerbation episode; between 7 and 14 days of the end of a period of exacerbation and at

	Where?	Completed by?	Consent visit	Baseline (intervention) visit	At clinic visits	Exacerbations episode	12 months from consent visit	
Enrolment			5	E E	₹	 	77 5	
Pre-screening form (before 1st visit)	Prospect	Site	-	-	-	-	-	
Confirmation of eligibility form	Prospect	Site	•	_	_	-	_	
Informed consent	Prospect	Site	•	_	_	-	-	
Intravenous days in last registry year	Prospect	Site	•	_	_	-	-	
Pseudomonas status +	Prospect	Site	•	-	-	-	-	
Primary outcome	Trospect							
Exacerbations form including:	Prospect	Site	•	-	-	•	•	
Parenteral antibiotics								
Change in sputum*								
New or increased hemoptysis*								
Increased cough*								
Increased dyspnea*								
Malaise, fatigue, or lethargy*								
Temperature above 38 °C*								
Anorexia or weight loss*								
Sinus pain or tenderness*								
Change: sinus discharge*								
Change: phys. exam. chest*								
Decrease: pulmonary function *								
Indicative radiographic changes*								
Secondary outcomes								
BMI (height and weight)	Prospect	Site	•	_	_	-	•	
FEV ₁	Prospect	Site	•	_	•	_	•	
EQ-5D-5L**	Prospect	PWCF	•	_	•	•	•	
PAM-13 (Health Style Assessment)	Prospect	PWCF	•	_		_	•	
Assessment of Routine	Prospect	PWCF	•	_	_	_	•	
SRBAI	Prospect	PWCF	•	_	_	_	•	
CFQ-R	Prospect	PWCF	•	_	_	_	•	
PHQ-8	Prospect	PWCF	•	_	_	-	•	
GAD-7	Prospect	PWCF	•	_	_	_	•	
MAD-3 (Medication Adherence Data-3 items)	Prospect	PWCF	•	-		_	•	
COM-BMQ	Prospect	PWCF	•	_		-	•	
Objective adherence	СЕНН	CFHH	•	-	-	-	•	
Subjective adherence single question	Prospect	PWCF	•	-	•	-	•	
Concomitant medications	Prospect	Site	•	-		_	•	
Other SAEs	Prospect	Site			-	_	•	
Resource use	Prospect	Site	-	-	_	-	•	
Behavioural question	Prospect	Site	•				•	
Behavioural questionnaire	Prospect	Site			•			
penaviourai questionnaire	Trospect	SILE						

every standard clinic visit. Where participants have not attended the hospital for a period of over 3 months, the Interventionist will administer the Clinic visit behavioural questionnaire and the EQ5D-5L over the phone every 3 months.

Table 4. CFHealthHub data (CFHealthHub group only)

	Completed by?	Baseline (intervention) visit	At intervention visit s with interventionist	Between sessions	At clinic visits	At 12 months
Clinician metrics						
Adherence data*	PWCF	•	•	•	•	•
Recommendation of modules by interventionist	Interventionist	•	•	-	•	-
Feed back to participant their adherence data screens (data click)	Interventionist	•	•	-	•	-
Check prescription with participant	Interventionist	•	•	-	•	-
Order of clicks	CFHH	•	•	-	•	-
Interventionist responds to patient changing prescription	Interventionist	-	•	•	•	•
Monthly check on prescription +	Interventionist / CTRU	•	•	•	•	•
Time in and out preparation	Interventionist /CFHH	•	•	-	-	•
Time in and out with patient	Interventionist /CFHH	•	•	-	-	•
Time in and out review	Interventionist /CFHH	•	•	-	-	•
Patient metrics						
Adherence (number of nebulized doses taken per day.) ¹	PWCF	•	•	•	•	•
Duration of inhalation	Nebuliser	•	•	-	-	-
Accessing CFHealthHub – look at adherence data	PWCF	•	•	-	-	-
Accessing CFHealthHub – look at 'My Toolkit'	PWCF	•	•	-	-	-
Accessing CFHealthHub problem solving / education / talking heads pages outside of 'My Toolkit'	PWCF	•	•	-	-	=
Accessing CF HealthHub – first to last click in a session	PWCF	•	•		-	-
	PWCF					X

^{*}Adherence data collected for both research and control arms

Data at the 12 month follow up visit may be collected by the interventionist within+/-4 weeks of the due date.

⁺ Monthly prescription checked by CTRU centrally to alert local interventionists to any potential changes

¹To be broken down in statistical analysis plan.

Figure 6. Participant timeline for the external pilot RCT Identification and approach, by letter, following up with phone call (pre-Consent form): 1) PWCF identified through the CF registry 2) Screened for eligibility (pre-screening tool): Inclusion: PWCF who have data within the CF registry aged > 16 years and taking inhaled mucolytics or antibiotics via a chipped nebuliser (e.g eTrack or I-Neb) or able and willing to take via eTrack or I-Neb. Exclusion: PWCF who are post-lung transplant or on the active lung transplant list, patients receiving palliative care, with palliative intent, for whom trial participation could be a burden, patients lacking in capacity to give informed consent or using dry Enrollment powder devices to take antibiotics or mucolytics. 3) Direct care team 1) Sends potential participant PIS and introductory letter by post and Interventionist follow's up by phone within 1 week to ensure they have received the information and allow an opportunity for questions AND/OR 2) Direct care team gives patients written information during routine clinic visit and asks permission to follow up the patient with a phone call to answer further questions and discuss involvement. CONSENT VISIT, at home or in clinic: 1) Screening form completed (confirmation of eligibility) 2) Informed consent 3) Data Collection: Intravenous days in last registry year; BMI; FEV1; EQ-5D-5L; PAM-13; CHAOS; MAD-3; SRBAI; CFQ-R; PHQ-8; GAD-7; COM-BMQ; Exacerbations form; subjective adherence question Participant given data logging nebuliser and Qualcomm hub. Randomisation (n~556): ACtiF interventionists randomises using web-based system between consent and baseline visits and informs participant ideally within 1 week of consent visit. Intervention arm Allocation Research: Monitoring and feedback (N=278): Initial Intervention visit: at home or in clinic (2-6 weeks from consent visit) (1 hour) 1) Adherence data uploaded, fed back and reasons for suboptimal adherence discussed in order to identify problems to solve using the Adherence Support Process; Control arm 2) Intervention chosen based on barrier from "library" in the Usual care n=278: Adherence Support Process; Adherence data uploaded. Care team and PWCF remain 3) Supportive contact offered via phone or email; and, blind to adherence data 4) Participants given personal access to CFHealthHub Manualised intervention delivered by trained researcher in initial intervention visit and subsequent visits normally every 4-6 weeks from this initial visit till six months visit (see below) ACtiF Researcher collects exacerbation data Data collected: Exacerbations form triggered by commencement of IV antibiotics; EQ5D-5L at both start and end of exacerbation episode Routine Clinic Visits: Data collected from all routine clinic visits after the date of consent. Follow-up Data collected by ACtiF researcher except where specified: (i) FEV1; (ii) subjective adherence question (iii) exacerbations form (iv) EQ5D-5L (v) Behavioural questionnaire. Adherence data continued to be uploaded to CFHealthHub Monthly follow up by CTRU researcher and/or ACtiF interventionist Monthly check of adherence data and contact with participant where missing adherence data or requirement to follow up on changes to prescription 12 month visit Primary clinical outcome: Number of exacerbations (Fuchs criteria) Secondary outcomes: BMI; FEV1; EQ-5D-5L; PAM-13; CHAOS; MAD-3; SRBAI; CFQ-r; PHQ-8; GAD-7; COM-BMQ; Exacerbations form; Other SAE's, resource use questionnaire

Interventionists should make every effort to collect secondary outcome data at 12m (-2w to +4w). However, data which comes in afterwards will be used in the analysis and will not be considered a protocol non-compliance.

8. Sampling

8.1 Quantitative components

8.1.1 Sites

Up to 20 specialist CF centres have been screened for their ability to recruit participants based on the number of participants they have on their CF registry and their motivation to participate in the main RCT.

8.1.2 Sample size

The sample size from the main trial has been revised from n=688 to n=556. The primary outcome measure will be the mean number of Pulmonary Exacerbations (PE) per patient treated with IV antibiotics that meet at least one of the Fuch's criteria in the 12 month post-randomisation follow-up. We shall use the Fuch's criteria for defining a PE in patients with CF, as used in the trials by Elkins et al and McIIwaine et al. The Elkin's et al trial, with 162 patients with CF, using a stricter definition of PE of exacerbations requiring IV antibiotic therapy plus 4 out of 12 of the Fuch's criteria reported a mean number of exacerbations over 48 weeks of 0.89 and 0.39 respectively in the control and intervention groups, a difference of 0.5 (95% CI: 0.14 to 0.86), with an estimated standard deviation of 1.2.

Based on the pilot data with six months' follow-up we observed 60 exacerbations in 60 patients; a mean of 60/60 = 1 exacerbation per patient; extrapolating this to 12 months gives a mean of 2 exacerbations per year; assuming the number of exacerbations in a year follows a Poisson distribution then the standard deviation is 1.5 (rounded up).

At an individual patient level we can only observe integer values for the number of exacerbations per year (e.g. 0, 1, 2, 3 etc.) and the smallest difference an individual patient can have is a change of one exacerbation per year. At a group or population level smaller differences than one exacerbation per year are likely to be clinically or practically important. Our original sample size calculation assumed a target difference of 0.9 exacerbations per year based on an average of around 3 exacerbations a year and made an allowance for contamination at the treating centre level of around 10% i.e. a likely reduction in the target difference of around 10% to allow for contamination effects at the centre (i.e. from 1.0 to 0.9 exacerbations per year). A reduction of 1 exacerbation per year is around 33% of the originally assumed baseline level of 3 exacerbations per year. With a lower baseline level of around 2 exacerbations per year a 33% reduction would equate to a reduction of difference of 0.66 exacerbations per year. If we allow for contamination at the treating centre level (of around 24% reduction in the target difference) and assume a smaller target difference of 0.5 exacerbations per year is of clinical and practical importance.

Therefore assuming a mean difference of 0.5 PE over a 1 year follow-up between the intervention and control groups is the target difference we wish to detect; a SD of 1.5; 90% power and two-sided significance level of 5%; a design effect of 1.16 to allow for any clustering of outcomes by physiotherapist (ICC of 0.01 and cluster size of 17) then we require 222 subjects per arm (444 in total) to detect this difference. If we assume a 20% loss to follow-up by 12 months then we would need to recruit 556 patients (278 per arm). Meta-analysis level evidence indicates that date and time stamped data improves adherence. Patients recruited to the active limb of the trial will receive feedback of time and dated stamped adherence data which the meta-analysis evidence suggest will be beneficial. We have been provided with sufficient funded chipped nebulisers to allow us to recruit up to 35 patients in each centre which may allow us to exceed our study targets based on our power calculations. We consider that it is in patients best interests to recruit them if the opportunity arises since the evidence suggests this will benefit their adherence and RCT evidence supports that the treatments prescribed are beneficial. In addition power calculations are an inexact since so increasing

our power will reduce the chance of a false negative trial result. Thus since over recruitment is associated with patient benefit we think that if the opportunity arises we should do this.

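### The 90% power in section 8.1.2 holds only if exacerbation counts are close to Poisson, and the one data-based SD the protocol cites is well above Poisson

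*Protocol*

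**What the plan says.** Protocol section 8.1.2 builds the SD in two steps. The pilot supplies the mean: "Based on the pilot data with six months' follow-up we observed 60 exacerbations in 60 patients", and "extrapolating this to 12 months gives a mean of 2 exacerbations per year". The SD then follows from the distribution and not from the pilot counts: "assuming the number of exacerbations in a year follows a Poisson distribution then the standard deviation is 1.5 (rounded up"). No pilot SD or variance is given.

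The calculation proceeds by "assuming a mean difference of 0.5 PE over a 1 year follow-up between the intervention and control groups is the target difference", with "a SD of 1.5; 90% power and two-sided significance level of 5" per cent. A design effect of 1.16 (ICC 0.01, cluster size 17) leads to 222 per arm, 444 in total. A 20% loss brings recruitment to 278 per arm, 556 in total.

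The same section cites an earlier CF trial of 162 patients, which "reported a mean number of exacerbations over 48 weeks of 0.89 and 0.39 respectively in the control and intervention groups". The protocol puts the 95% confidence limits for that trial's 0.5 difference at 0.14 and 0.86, and its SD at 1.2. It also notes that this trial used a stricter definition of exacerbation: IV antibiotics plus 4 of the 12 criteria, where the present trial needs one.

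**The concern.** A Poisson count has variance equal to its mean, which requires all patients in an arm to share one underlying rate. The cited trial does not look like that. Poisson counts at its arm means would have SDs of about 0.94 and 0.62, against the quoted 1.2. Section 9.1 also stratifies randomisation by IV days in the previous year, which suggests that the investigators expect patients to differ in underlying rate.

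Power depends directly on the SD, and section 8.1.2 gives one value with no sensitivity range. If the true SD is materially above 1.5, a null result would be read as a 90%-powered exclusion of a 0.5 reduction when the trial had a considerably lower chance of detecting it.

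**Working it through.** **Inputs (all from section 8.1.2).** Difference 0.5; SD 1.5; two-sided 5%; power 90%; design effect 1.16; 222 evaluable per arm; loss 20%; control mean 2, so intervention mean 1.5 and average 1.75. Cited trial: means 0.89 and 0.39 (average 0.64), SD 1.2, CI 0.14 to 0.86, N = 162. An equal split of 81 per arm is my assumption.

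**Step 1: reproduce the plan.** n per arm = 2 × (1.960 + 1.282)² × 1.5² / 0.5² = 189.1, so 190, or 191 with the t distribution. 191 × 1.16 = 221.6, so 222. 222 / 0.8 = 277.5, so 278 per arm and 556 in total. Effective n = 222 / 1.16 = 191.4 per arm. Power = Φ(0.5 / (SD × √(2/191.4)) − 1.96), which at SD 1.5 is 90.3%. The plan's figures reproduce.

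**Step 2: dispersion allowed by the plan.** 1.5² / 2 = 2.25 / 2 = 1.125 times Poisson at mean 2.

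**Step 3: dispersion in the cited trial.**
- From the stated SD: 1.2² = 1.44; 1.44 / 0.64 = 2.25.
- From the CI: SE = (0.86 − 0.14) / 3.92 = 0.184; SD = 0.184 / √(2/81) = 1.17; variance 1.37; 1.37 / 0.64 = 2.13.
- Against the control mean alone: 1.44 / 0.89 = 1.62, or 1.37 / 0.89 = 1.54.
- Negative binomial, variance = mean + k × mean², fitted to the two arms: k = (1.44 − 0.64) / [(0.89² + 0.39²) / 2] = 0.80 / 0.472 = 1.70. With the CI-derived SD, k = 1.54.

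**Step 4: carry each over to this trial, 222 per arm, difference 0.5.** The ratio readings use variance = ratio × mean, at mean 1.75 and at mean 2. The constant-k reading uses average variance = 1.75 + k × (2² + 1.5²) / 2 = 1.75 + 3.125k. The last column is (1.960 + 1.282) × SD × √(2/191.4) = 0.331 × SD.

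| Reading | SD | Power | Difference detectable at 90% |
|---|---|---|---|
| Plan | 1.50 | 90% | 0.50 |
| Ratio to control mean, 1.54–1.62 (most lenient) | 1.64–1.80 | 78–85% | 0.54–0.60 |
| Ratio to average mean, 2.13–2.25 | 1.93–2.12 | 64–72% | 0.64–0.70 |
| Constant k, 1.54–1.70 | 2.56–2.65 | 45–48% | 0.85–0.88 |

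A negative binomial Wald test on the log rate ratio, log(1.5/2), gives much the same: about 70–72% at the constant ratio (mean 1.75) and about 46–49% at these values of k.

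**Step 5: what could recover power.**
- Primary outcome obtained on all 278 per arm: 79–81% at SD 1.93–1.98, 54–57% at SD 2.56–2.65.
- 700 recruited (20 centres × 35) with complete outcomes: 87–89% at SD 1.93–1.98.
- Covariates explaining 20–40% of variance (assumed), 222 per arm: about 79–91% at the constant ratio, 53–65% at constant negative binomial dispersion.

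**The case against.** The strongest reply is that the contrary SD is not this trial's. It comes from a trial with a stricter definition, 48 weeks of follow-up and means below 1. That stands: carrying its dispersion over is an extrapolation, and the true SD here is unknown from the protocol. It does not rescue 1.5, because that value has no empirical support in the protocol either.

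Second, rounding up gives some slack: 1.125 times Poisson at mean 2, or 2.25 / 1.75 = 1.29 times at the average mean. True, but it falls short of even the most lenient ratio, 1.54.

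Third, the 20% loss may be pessimistic for this outcome. Section 6.6 plans to go on collecting exacerbations from notes unless a patient withdraws entirely, and section 8.1.2 allows up to 35 patients per centre and concedes that power calculations are inexact. Adjustment for prior IV days could also help. These points stand in part. With all 278 per arm, the most lenient reading gives about 86–92%, so the target can be reached. But section 8.1.2 claims none of these gains; its 90% is for an unadjusted comparison at 222 per arm.

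Three stronger inferences are tempting and not supported:
- *The revision halved the SD simply by ignoring heterogeneity.* Section 8.1.2 says "The sample size from the main trial has been revised from n=688 to n=556". One can back-solve an SD near 3.0 from 688 and a difference of 0.9, but only by assuming 90% power, 20% loss and a design effect of 1.16, none of which is stated for the superseded calculation. The assumed mean also fell from 3 to 2.
- *A Poisson analysis will inflate type I error.* The protocol names no model for the primary outcome, and the SAP may do so.
- *The pilot variance was looked at and set aside.* The protocol does not say whether it was examined.

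**Conclusion.** The point holds as a weakness in an input, not as an error of arithmetic. The stated 90% power requires nearly Poisson counts, and the only SD from data in the same section points to clear overdispersion. On every unadjusted reading at the planned 222 per arm, power is below 90%: about 64–72% if the variance-to-mean ratio of about 2.1 to 2.25 carries over, about 78–85% on the most lenient reading, and about 45–48% at constant negative binomial dispersion.

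A reader might conclude that the trial has less than even odds of detecting its target. The documents do not establish that. The lowest range needs a dispersion parameter from rarer, more strictly defined events to apply unchanged at about twice the control rate or more. All the ranges rest on the cited trial's dispersion applying here, on the equal split where the CI is used, and on the full 20% loss of primary outcomes.

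**What to change.** In section 8.1.2, replace the Poisson SD with the SD or dispersion observed in the pilot counts. Then state the power at 556, or the difference detectable with 90% power (about 0.64–0.70 at SD 1.93–2.12), over a stated range of dispersion, since 60 patients will estimate it imprecisely.

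The pilot counts cover six months, so the conversion to 12 months should be shown. If patients keep stable individual rates, k can be taken from the six-month variance s² as (s² − 1) / 1², and the 12-month control variance is 2 + 4k. Any gain claimed from outcome collection through notes, over-recruitment or covariate adjustment should appear as a separate line with its assumption.

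The cost is one calculation, assuming the pilot counts are still held, and a rewording of one section. No extra patients are needed. The price is a stated power that is likely to be less favourable.

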8.1.3 Approach, non-participation and recruitment

Approach: Health professionals involved in approaching and screening PWCF and collecting data will be trained in the study protocol and procedures. Additionally those taking consent will have up-to-date training in Good Clinical Practice (GCP). All study personnel will be named on the study delegation log. Health professionals working with the CF team will identify a sample of PWCF registered at the centre via the CF registry database locally. The CF Clinical team member at each site will send an encrypted excel file containing Registry number, gender, age and number of IV days (in home and hospital), via email to the Sheffield CTRU Study Manager; the password will be communicated separately via a telephone call. The encrypted excel file will be saved on an access restricted University Network Folder; it will be unencrypted and uploaded to Prospect. Alternatively, each site will be able to input screening information directly into Prospect from their CF registry data. All inclusion and exclusion criteria will be assessable via patient records and they will exclude any patients who do not fit the eligibility criteria.

A member of the participant's direct clinical team will send the potential participant a PIS and introductory letter by post or give the written information during a routine clinic visit. If information is provided in a routine clinic visit, the clinical care team will seek permission for the ACtiF Interventionist to follow up with a phone call in order to answer any further questions and discuss involvement. Written informed consent may be conducted at this visit where the participant is happy to take part as this is a low risk trial.

Telephone call: Up to a week after posting out the information, the ACtiF Interventionist will telephone or text the PWCF to discuss the study over the phone and answer any questions. If the potential participant is happy to take part, the ACtiF Interventionist will arrange an appointment to gather written informed consent.

Non-participation: Spontaneously offered reasons for non-participation in the trial will be recorded.

8.2 Qualitative components

All intervention visits in each centre will be audio recorded with permission from the patient to assess the fidelity of implementation of the intervention and mechanisms of action throughout the trial. Encrypted digital recorders will be used at each site and recordings sent securely to the research team for analysis.

- Interview with the interventionist in each centre (n=20)
- Interviews with 16-20 PWCF: 8-10 PWCF within 2-3 months of starting the intervention to explore changes made since the pilot and 8-10 PWCF 6-12 months after being introduced to the intervention to understand their views of the intervention in the longer term
- Interviews with 6-8 PIs sampled based on sites with specific issues e.g. not recruiting, large number of withdrawals to understand how the context may impact the RCT and/or intervention

Written informed consent will be obtained from both the interventionist and the PWCF participating in the audio recording when they consent to be in the study. Separate consent will be sought from PWCF, interventionists and PIs for semi-structured interviews.

9. Assignment of interventions

9.1 Sequence generation

Participants will be allocated in equal proportions to one of the two groups using a computer generated pseudo-random list, stratified by centre and the number of days participants have been on IV antibiotics in the previous 12 month period as collected at consent visit, with random permuted blocks of varying sizes. The two categories for stratification within the number of IV days will be (i) less than or equal to 14 days and (ii) greater than 14 days.

